8.2.3. Safety analysis

All adverse reactions and adverse events occurring after the start of administration of this drug will be summarized in listings. The listings will include all events reported in this study. Safety will be evaluated using all data collected after the start of administration of this drug without classifying the data into Vyndaqel and Vynmac unless otherwise specified was added.

8.2.3.1. Adverse reactions

8.2.3.1.1. All adverse reactions

The number and proportion of patients with adverse reactions will be tabulated by SOC and PT.

8.2.3.1.2. Serious adverse reactions

The number and proportion of patients with serious adverse reactions will be tabulated by SOC and PT.

8.2.3.1.3. Details of adverse reactions

The number and proportion of patients with adverse reactions will be tabulated by SOC and PT for each of the following items:

- Seriousness [serious, non-serious]
- Number of days to onset [<26 weeks, \geq 26 weeks and <52 weeks, \geq 52 weeks and <78 weeks, \geq 78 weeks and <104 weeks, \geq 104 weeks and <130 weeks, \geq 130 weeks] (For the tabulation of incidence, the number of patients receiving at least one dose of this drug in each period category will be used as the denominator.)
- Action taken [suspended, dose reduced, dose increased, discontinued]

- Outcome [recovered/resolved, recovering/resolving, recovered/resolved with sequelae, not recovered/not resolved, fatal, unknown]

For outcomes, the number and proportion of patients with serious adverse reactions will be tabulated by SOC and PT.

If the same adverse reaction (of the same PT) occurs more than once in the same patient, it will be handled as follows in the tabulation of the number of patients with events:

- Seriousness: If both serious and non-serious events are reported, the event will be regarded as serious.
- Number of days to onset: Defined as the number of days to the first event.
- Action taken: If multiple types of actions were taken, one action will be adopted in the order of priority of discontinued, suspended or dose reduced, and other (none, dose increased).
- Outcome: The outcome of the last occurring event will be used.

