#### **8.2.6. Observation period**

[figure not shown]
30 months (Week 130) from the start of administration (Day 1)

However, for patients who discontinued this drug during the observation period, the observation period will be until the first visit after the date of discontinuation.

[figure not shown]
In this study, information will be collected using a booklet type CRF. Information during the following periods will be entered in each booklet.

If the patient is transferred to another hospital or department (hereinafter referred to as hospital transfer) during the observation period, the patient will be newly registered even at the transferred site and the CRF will be completed. If the patient is transferred to another hospital, the patient registration number of the original site will be conveyed to the transferred site. Although the patient will be given a new patient registration number at the transferred site at the time of registration, he or she will be determined to be a transferred patient by reporting the patient registration number of the original site and his/her data will be handled as the same patient. If the time point of 30 months after the start date of initial administration can be identified for the transferred patient, the observation period at the transferred site may be reset so that the total observation period of the patient in this study will become 30 months.

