## 10.2. Reporting period

For each patient, the safety event reporting period begins at the time of the patient's first dose of this drug, and lasts through the end of the observation period of the study, which must include at least 28 calendar days following the last administration of a drug under study; a report must be submitted to Pfizer Safety (or its designated representative) for any of

PFIZER CONFIDENTIAL

CT24-WI-JPN-GPSP01-RF09 7.0 Non-Interventional Study Protocol Template for Secondary Data Collection

Study 15-Sep-2022

Page 28 of 39

the types of safety events listed in the table above occurring during this period. If a patient was administered a drug under study on the last day of the observation period, then the reporting period should be extended for 28 calendar days following the end of observation. If the investigator becomes aware of a SAE occurring at any time after completion of the study and s/he considers the SAE to be related to this drug, the SAE also must be reported to Pfizer Safety.

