5.0/ 28-May-2024/ PPD / Ongoing	
 • 2.1 The end date of the registration period was specified in association with the termination of registration only. In addition, the statement about registration only patients for investigation was deleted. • 5.1 The criteria for inclusion in the safety analysis set were added. • 5.2 The criteria for the efficacy evaluation in the efficacy analysis set and the description in the report were changed based on the latest version of the Guidance for Criteria for Inclusion in Analysis Sets and Data Handling in Use-result Surveys. • 5.3 The safety analysis set consisting of consented patients and the efficacy analysis set consisting of consented patients were added. • 5.4 Usage experience of this drug was added to and dose change was deleted from the subgroups. • 8.1.4 The method of handling a period data which includes interval-censored data was added. • 8.2 A description about the tabulation and analysis in the safety analysis set consisting of consented patients or the efficacy analysis set consisting of consented patients was added. • 8.2.1.1 The “Numbers of study sites and study patients by founder” section was deleted. • 8.2.1.1 The tabulation of patient disposition was changed from registered patients to patients with collected case report forms. • 8.2.2.1 The analysis sets for the breakdown of complications was changed to the safety analysis set only. In addition, the tabulation of the categories of concomitant medications was deleted. • 8.2.3 Adverse reactions and adverse events to be tabulated were changed from those occurring during the observation period to all of those collected. • 8.2.3.1.5 The “Relationship between concomitant medications and occurrence of adverse reactions” section was deleted. • 8.2.3.2.1 The “All adverse events” section was deleted. • 8.2.3.2.1 The section name was changed from “Serious adverse events” to “Adverse events by seriousness,” and the method of tabulation of non-serious adverse events was added. • 8.2.4.3 The period for the tabulation of the number and proportion of deaths was specified. • A1.1 The method of handling of multiple values of the same endpoint at the same visit time was added. • Other minor description modifications were made.

Version/ Date/ Author(s)/ Status of Study	Summary of Changes/Comments

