2.1. Study Design

Investigation period: March 2019 to September 2023 (From the start date of observation for the first subject to the end date of observation period for the last subject)

Registration period: March 2019 to March 2021 (From the start date of treatment for the first subject to the start date of observation period for the last subject)

Study patients: This study will be conducted with all patients surveillance system that all patients will be registered until data are collected on a target number of patients.

Target sample size: The number of patients with ATTR-CM in Japan is estimated to be approximately 750. Of these, the proportion of patients who actually received the definitive diagnosis and were prescribed with this drug was estimated to be approximately 40% (approximately 300 patients). As a result, the target sample size was set at 300 subjects from the viewpoint of feasibility. (300 patients to be evaluated for the safety of this drug)

Observation period: 30 months (Week 130) from the start of administration (Day 1). However, for patients who discontinued this drug during the observation period, the observation period will be until the first visit after the date of discontinuation.

Handling of patients transferred to another hospital or department: For the proper use of this drug, requirements for patients, institutions, and physicians have been specified by the Japanese Circulation Society¹, and it is necessary to meet all of these requirements to introduce this drug. However, since continued prescription at another institution is allowed in consideration of convenience, patients who have already started to receive this drug may be transferred to another hospital or department. If the patient is transferred to another hospital or department (hereinafter referred to as hospital transfer) during the observation period, the patient will be newly registered even at the transferred site and the CRF will be completed. If the patient is transferred to another hospital, the patient registration number of the original

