7. HANDLING OF MISSING DATA

If treatment with this drug is continued even after the end of the observation period and the end date of treatment is missing, the end date of observation will be handled as the end date of treatment in this study.

If the seriousness, causal relationship, and action taken and outcome regarding adverse events are missing, these data will be handled as “unknown” for tabulation.

For the efficacy endpoints and laboratory test values, if there is no measurement within the time window for each evaluation time point (Appendix 1), data will be handled as missing, and the missing data will not be complemented.

The strategy for handling data with uncompleted cleaning is described below:

- Items of missing data: The items will be handled as missing (category of categorical variables is “unknown”) for both tabulation and listing.
- Items of inconsistent data: The items will be handled as missing for both tabulation and listing. However, a list of data handling should be prepared separately.
- No signature: Any entry in a case report form without the signature of the contracted physician (including a case report form with the signature of an uncontracted physician only) will be handled as missing for both tabulation and listing. If there is no date of signature in the field for the date of signature or if there is inconsistency in the date entered (e.g., date before the start date of treatment, future date), the entry in the case report form will be regarded as having no signature.

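### In the time-to-onset table, adverse reactions after the last dose can be counted in a category whose denominator excludes the patient, and the ≥130 weeks percentage is not interpretable

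*SAP*

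**What the plan says.** SAP 8.2.3.1.3 tabulates patients with adverse reactions by SOC and PT in six onset categories: five of 26 weeks each, then ≥130 weeks. For incidence, "the number of patients receiving at least one dose of this drug in each period category will be used as the denominator". When a PT recurs in a patient, days to onset is "Defined as the number of days to the first event", so each patient contributes once per PT.

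The events that count are set in SAP 8.2.3: "Safety will be evaluated using all data collected after the start of administration of this drug". The SAP change log for version 5.0 agrees, describing the tabulated events as "changed from those occurring during the observation period to all of those collected". By contrast, the efficacy sentence in SAP 8.2.4 keeps the limit to the observation period.

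Planned observation is "30 months (Week 130) from the start of administration (Day 1" (SAP 2.1). For patients who stop the drug, "the observation period will be until the first visit after the date of discontinuation" (Protocol 8.2.6), with no fixed interval to that visit. Protocol 10.2 requires safety reporting for at least 28 days after the last dose. If a patient continues the drug beyond observation and the treatment end date is missing, "the end date of observation will be handled as the end date of treatment in this study" (SAP 7).

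**The concern.** The two halves of the fraction follow different rules. The denominator requires a dose within the category. The numerator requires only that the first onset falls within it, on or off drug. Off-drug onsets are collected by design, so some patients can appear in a numerator without being in the denominator.

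The last row has a second problem. It begins at the point where planned observation ends and has no upper limit, yet it would be printed beside five rows that each represent 26 weeks of use. The study objective is long-term safety, so a reader would naturally take that row as the incidence with the longest use. It cannot carry that meaning.

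**Working it through.** The plan gives no figure for this table. Its one calculated figure is the 98% chance of at least 10 hepatotoxicity cases in Protocol 8.5.2. It reproduces: P(X ≥ 10) for X ~ Binomial(300, 0.0588) is 0.984. The present point does not depend on it.

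**1. Boundary crossing.** Suppose a patient takes the last dose in Week 25, has a first onset of some PT in Week 28, and then has the first visit after discontinuation. The onset belongs to the category from 26 to under 52 weeks. The patient took no dose in that category, so the numerator gains 1 and the denominator gains 0. Had the onset come in Week 26 or earlier, it would have fallen in the category of the last dose and been matched. A reaction during an interruption is unmatched only if no dose was taken in the whole category.

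**2. How often a crossing could occur.** The lag to the first visit after stopping is not in the documents, so a range is assumed. Take stopping dates as uniform over a 182-day category and off-drug onsets as uniform over a lag of L days. The share of off-drug onsets landing in a later category is then L / (2 × 182).

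| Assumed lag L (days) | Share unmatched |
|---|---|
| 14 | 14/364 = 3.8% |
| 28 | 28/364 = 7.7% |
| 56 | 56/364 = 15.4% |
| 84 | 84/364 = 23.1% |

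These are shares of off-drug onsets, not of all reactions.

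**3. Planned exposure in the ≥130 weeks row.** 130 × 7 = 910 days. For every start date from 1 March 2019 to 31 March 2021, 30 calendar months is 911 to 915 days. For example, 1 March 2019 to 1 September 2021 is 731 + 184 = 915 days. The gap is therefore 1 to 5 days if observation closes at 30 calendar months, and about none if it closes at Week 130.

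With an assumed 200 completers, planned person-time in the row is 200 × 1/365.25 = 0.55 to 200 × 5/365.25 = 2.74 person-years. A full 26-week row with the same 200 patients holds 200 × 182/365.25 = 99.7.

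**4. Sensitivity to the day count.** Administration starts on Day 1. A dose on Day 910 is at 909 days if elapsed time is counted and 910 if Day 1 counts as one. The first falls below 130 weeks and the second does not. That choice, together with how sites close observation, can move the denominator from near zero to nearly all completers. With two late reactions (an assumed count), the row reads 2/5 = 40% or 2/200 = 1%.

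**5. The same boundary in months.** The treatment-period table (SAP 8.2.2.2) and the discontinuation table (SAP 8.2.1.2) cut at 30 months, with no stated conversion from days. Protocol Table 1 equates Month 12 with Week 52 and Month 30 with Week 130. Both give 52/12 = 130/30 = 4.333 weeks per month, on which 910 days is exactly 30.0 months. With an average month of 30.4375 days, 910 days is 29.90 months. The side on which a Week 130 completer falls depends on a rule that the SAP does not give.

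**The case against.** The strongest reply is that the rule is stated openly, that counting patients dosed in the period is a recognisable convention, and that little depends on it. SAP 4 describes the study as non-confirmatory. The main adverse reaction proportion uses the whole safety analysis set (Protocol 8.7). Most off-drug onsets would be matched under the shorter lags above. All of this stands, and it limits the size of the point. It does not make the fraction a proportion or the last row readable.

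Some stronger readings are tempting but not supported:

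- **Every row divides all reactions collected by that period's patients.** It does not. A row counts only patients whose first onset of the PT falls in it.
- **This is the only planned display of timing.** SAP 8.2.3.1.4 sends the safety specifications to Section 8.1.4, which is Kaplan-Meier time to onset. If the person-years method in 8.1.6 was meant, a rate is planned. Onset is also evaluated by product period (SAP 8.2.3.3).
- **Later rows are inflated.** The direction is not established. Unmatched onsets raise a row. Patients who already had the PT stay in the denominator although they cannot count again, which lowers it.
- **Related SAEs reported after the study enter the table.** Protocol 10.2 covers the case "If the investigator becomes aware of a SAE occurring at any time after completion of the study" and requires a report to the sponsor's safety function if the investigator considers the event related. CRF collection of adverse events stops at the end of observation or the first visit after discontinuation (Protocol 8.3.8). Entry into the table is only an inference from the wording of SAP 8.2.3.
- **Nobody has real exposure after Week 130.** SAP 7 replaces only missing end dates. The SAP also allows for later records, with ≥30 months categories and a Month 30 window running to 39 months. Actual dosing past Week 130 cannot be determined from the documents.

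**Conclusion.** The point holds as a defect of definition. Under the current text, an onset after the last dose that crosses a category boundary is in the numerator and not the denominator. The ≥130 weeks row has about 0 to 5 planned days of exposure per completer, and its percentage cannot be read as long-term incidence.

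The number of affected reactions is unknown. The 4% to 23% range rests on assumed lags and uniform timing, and the 40% against 1% contrast on assumed counts.

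A reader might go further and call the last row meaningless, or conclude that completers are misplaced in the treatment-period row from 24 to under 30 months. Neither follows. With an explicit day rule the row has a denominator, and on the protocol's own scale 910 days is exactly 30 months. What is shown is that the convention is missing. The overall adverse reaction proportion is unaffected. The point merits correction because the table bears directly on the long-term safety objective and the repair is cheap.

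**What to change.** 1. In SAP 8.2.3.1.3, use as denominator the patients still under observation at the start of each category, whether on drug, interrupted or awaiting the first visit after discontinuation. Preferably also require them to be free of that PT, since only first events count. SAP 8.1.6 already runs exposure to the last observation for patients with no event, so this brings the two analyses closer. Alternatively, restrict the numerator to onsets within a stated window after the last dose and define the denominator by the same window.
2. Report onsets after the end of observation, including the ≥130 weeks row, as counts and in the listing, without a percentage.
3. State one day-count convention for the Week 130 / 30-month boundary and apply it to the onset, treatment-period and discontinuation tables.

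The cost is SAP wording and programming, with no new data. A PT-free denominator differs for each PT, which makes the table somewhat heavier. The last row loses its percentage.

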8.2.3.1.4. Safety specifications

For the safety specifications shown in Section 6.1, the number and proportion of patients will be tabulated. The number and proportion of patients with safety specifications will be tabulated by SOC and PT for each action taken and outcome.

In addition, safety specifications will be analyzed, taking into account the difference in exposure period, as described in Section 8.1.4.

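### When a preferred term recurs in a patient, the table of serious adverse reactions by outcome can report a non-serious episode's outcome as that of the serious reaction

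*SAP*

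**What the plan says.** SAP 8.2.3.1.3 gives a set of rules for repeats, introduced by "If the same adverse reaction (of the same PT) occurs more than once in the same patient, it will be handled as follows". They apply to tabulations that count patients with events. Each attribute has its own rule:

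- Seriousness, any serious episode decides: "Seriousness: If both serious and non-serious events are reported, the event will be regarded as serious".
- Onset, first episode: "Number of days to onset: Defined as the number of days to the first event".
- Action taken, priority order: "If multiple types of actions were taken, one action will be adopted in the order of priority of discontinued, suspended or dose reduced".
- Outcome, last episode: "Outcome: The outcome of the last occurring event will be used".

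Outcome has six categories: "Outcome [recovered/resolved, recovering/resolving, recovered/resolved with sequelae, not recovered/not resolved, fatal, unknown". The section also crosses outcome with seriousness: "For outcomes, the number and proportion of patients with serious adverse reactions will be tabulated by SOC and PT". The SAP's amendment table shows that this last tabulation was added in version 6.0.

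SAP 8.2.3.1.4 has another table that uses outcome: "The number and proportion of patients with safety specifications will be tabulated by SOC and PT for each action taken and outcome". It states no rule for repeats and does not refer back to 8.2.3.1.3.

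**The concern.** Most of the by-item tables use one attribute at a time, so it does little harm that onset, action and outcome come from different episodes. The serious-by-outcome table is different because it crosses two attributes. Seriousness may come from one episode and outcome from another, and nothing in the outcome rule confines it to episodes that were serious. The resulting cell can describe a reaction that did not occur.

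The study's stated objective is long-term safety, and Protocol 8.9 acknowledges that there is no control group. Readers will therefore rely on descriptive tables of this kind to see how serious reactions ended.

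**Working it through.** No figure in the plan bears on this point. Its one probability statement (Protocol 8.5.2: at least 10 hepatotoxicity cases among 300 patients at 5.88%, about 98%) reproduces at 0.984 by the exact binomial, but nothing here depends on it. The check is to apply the written rules to episode histories.

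**Worked cases (two episodes of one PT in one patient)**

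| Episode 1 | Episode 2 | Cell under the rules as written | Cell using serious episodes only, last one |
|---|---|---|---|
| serious, not recovered | non-serious, recovered | serious / recovered | serious / not recovered |
| serious, recovered | non-serious, not recovered | serious / not recovered | serious / recovered |
| non-serious, recovered | serious, not recovered | serious / not recovered | serious / not recovered |
| serious, not recovered | serious, recovered | serious / recovered | serious / recovered |

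The first two rows are mispaired, in opposite directions. The third is correct. In the fourth the outcome does belong to a serious episode, so which serious episode to report is a matter of choice.

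**Counting all two-episode histories**

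Inputs: two levels of seriousness and the six outcome categories of SAP 8.2.3.1.3. Assumptions: a fatal outcome can occur only in the last episode, and a fatal episode is serious. Episode 1 then has 5 possible outcomes. Episode 2 has 6 if serious and 5 if not.

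- Episode 2 serious: 2 × 5 × 6 = 60. Episode 2 non-serious: 2 × 5 × 5 = 50. Total 110.
- Neither episode serious: 5 × 5 = 25. Classed serious: 110 − 25 = 85.
- Serious, then non-serious: 5 × 5 = 25. In all of these the reported outcome comes from the non-serious episode.
- Of those 25, both outcomes agree in 5, so the cell is wrong for the serious reaction in 25 − 5 = 20.
- Of those 20, a serious episode that was not recovered or left sequelae appears as recovered or recovering in 2 × 2 = 4. The reverse also occurs in 2 × 2 = 4.

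These count possible patterns and give no frequency.

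**Effect on one row**

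The documents do not give the number of serious cases per PT. If a row held 2 or 3 patients (an assumption), one misassigned patient would move 1/2 = 50% or 1/3 = 33% of that row to another outcome category.

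**The case against.** The strongest defence is that SAP 6.1 defines serious adverse reactions by the physician's assessment of the event. A programmer could select serious events first and then take the last of them, and the mispairing would vanish. That is a possible reading, but the repeat rule does not state it. Read literally, the rule classes the collapsed record as serious and assigns it the last episode's outcome. Two competent programmers could produce different tables.

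Second, last status is a legitimate patient-level summary. Protocol 10.3 requires drug-related events to be followed until they resolve or stabilise, and separate rules for onset, action and outcome are ordinary practice. This stands, and it is why a full worst-outcome ranking is not required. A reader might infer one from the priority order used for action taken. However, an action is something that happened, while an outcome is a status that changes. A ranking also brings its own problems, such as whether an unknown outcome should override a known recovery. None of this justifies using the status of a different, non-serious episode for the serious one.

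Third, SAP 8.2.3 says the listings will contain every reported event, and SAP 9 includes a listing of patients with serious adverse reactions, so each case can be checked. This limits the harm but does not correct the table.

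**Conclusion.** The point holds in a limited form. As written, the serious-by-outcome table can show a non-serious episode's outcome as that of the serious reaction. This needs a patient with both serious and non-serious episodes of the same PT, a non-serious episode last, and differing outcomes. Such patients are probably few, and the documents do not allow a count.

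Three stronger readings are tempting but unsupported:

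- **That the error mostly favours the drug.** The patterns are symmetric (4 against 4 in the count above). The documents do not say how non-serious recurrences end, and the adverse event items in Protocol 8.3.8 record seriousness but not severity. A fatal outcome would be the last event and is unlikely to be overwritten.
- **That a given share of the table is misclassified.** For example, 5% of 300 patients gives 15 with a serious reaction, and 1 to 3 discordant recurrences among them gives 1/15 to 3/15, or 7% to 20%. Both inputs are assumed, so the result only restates them.
- **That the safety-specification table has the same defect.** SAP 8.2.3.1.4 has no repeat rule, so whether the last-event rule carries over is an inference.

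**What to change.** In SAP 8.2.3.1.3, state that in the table of serious adverse reactions by outcome, the outcome is taken only from the patient's serious episodes of that PT. If the sponsor keeps the last-event rule, this means the last serious episode. In SAP 8.2.3.1.4, state whether the repeat rules of 8.2.3.1.3 apply to the outcome table there.

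Where several serious episodes remain, the sponsor may choose a worst-outcome priority instead of the last. That is an option and not a needed correction.

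The correction in 8.2.3.1.3 costs one sentence and a filter in the program. Protocol 8.3.8 already has seriousness and outcome recorded for adverse events, so no new data are needed. The downside is that the outcome of a later non-serious episode will then appear only in the all-reactions table and the listings.
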